5.3.2. Achieving and Sustaining Remission of Depressive Symptoms

5.3.2.1. Definition

A secondary efficacy endpoint is the proportion of subjects achieving (at Week 12) and sustaining remission at Weeks 18 and 24. Remission is defined as MADRS total score ≤ 12 . A subject must have a MADRS total score ≤ 12 at all 3 time points (Week 12, Week 18, and Week 24) to be defined as a sustained remitter. Subjects who do not meet such criterion will be considered as non-sustained remitters. The calculation of the MADRS total score is described in Section 5.3.1.1.

5.3.2.2. Analysis Methods

The number and percentage of subjects who achieve and sustain remission will be summarized by treatment group. In addition, the number and percentage of subjects who have a MADRS total score ≤ 12 at each postbaseline time point will be presented by treatment group.

The point estimate and 2-sided 80% confidence interval will be provided for the relative risk of achieving and sustaining remission using a Mantel-Haenszel test controlling for baseline insomnia status (present/absent).

5.3.3. Achieving and Sustaining Response of Depressive Symptoms

5.3.3.1. Definition

A secondary efficacy endpoint is the proportion of subjects achieving (at Week 12) and sustaining response at Weeks 18 and 24. Response is defined as $\geq 50\%$ improvement from baseline MADRS total score. A subject must have a $\geq 50\%$ improvement from baseline MADRS total score at all 3 time points (Week 12, Week 18, and Week 24) to be defined as a sustained responder (yes=1). Subjects who do not meet such criterion will be considered as non-sustained responders and will be assigned a value of 0 (i.e., no). The calculation of the MADRS total score is described in Section 5.3.1.1. The percentage change from baseline for MADRS total score is calculated as $100 * (\text{MADRS total score at Week X} - \text{Baseline MADRS total score}) / (\text{Baseline MADRS total score})$. Negative percent changes in MADRS total score indicate improvement (e.g., percent change $< -50\%$ indicates improvement $> 50\%$).

5.3.3.2. Analysis Methods

The number and percentage of subjects who achieve and sustain a response will be summarized by treatment group. In addition, the number and percentage of subjects who have a $\geq 50\%$

improvement from baseline MADRS total score at each postbaseline time point will be presented by treatment group.

The point estimate and 2-sided 80% confidence interval will be provided for the relative sustained response using a Mantel-Haenszel test controlling for baseline insomnia status (present/absent).

The cumulative response rate, defined as the percentage of subjects experiencing at least a given value of percent reduction from baseline to Week 24 in MADRS total score, will be presented graphically, for both observed and LOCF data.

The cumulative distribution function of the time to sustained response will be estimated by the Kaplan-Meier method. Time to sustained response will be summarized (number of sustained responders, number of censored subjects, median, 25th and 75th percentile, if estimable) by treatment group. Sustained response is defined as the first occurrence of response that is maintained through the Week 24 assessment. Subjects who discontinue early are not considered to have sustained response. A stratified log rank test (stratified for baseline insomnia status) will be used to test the hypothesis that there is no difference between JNJ-42847922 and quetiapine XR in the probability of achieving sustained response. In addition, time to sustained response will be summarized by modal dose.

5.3.4. Change in Hamilton Anxiety Rating Scale (HAM-A)

5.3.4.1. Definition

A secondary efficacy endpoint is the change from baseline to Weeks 12, 18, and 24 in the HAM-A total score. The original 14-item clinician-administered HAM-A scale assesses the severity of different anxiety-related symptoms. It is a commonly used, validated scale in clinical trials assessing anxiety. However, the original HAM-A lacks instructions for administration and clear anchor points for the assignment of severity ratings. For this reason, the structured interview guide version (SIGH-A) will be used in this study.

Each of the 14-items in the scale is scored on a 5-point scale, ranging from 0 (not present) to 4 (very severe, symptom is incapacitating). A total score (0 to 56) is calculated by adding the scores of all 14 items, where 0-13 indicates normal range, 14-17 indicates mild severity, 18-24 mild to moderate severity, 25-30 moderate to severe, and ≥ 31 severe. Higher scores represent a more severe condition.

The HAM-A change from baseline at Week 24 is calculated as (HAM-A total score at Week 24 – Baseline HAM-A total score). Change from baseline to other time points is calculated similarly. Negative changes in HAM-A total score indicate improvement.

The somatic factor score of HAM-A is defined as the sum of items 7 to 13; and the psychic factor score of HAM-A is defined as the sum of items 1-6 and 14.

5.3.4.2. Analysis Methods

Descriptive statistics of the actual values on Baseline, Week 6, Week 12, Week 18, Week 24, and at follow-up and the change from baseline to each postbaseline time point will be presented for HAM-A total score, and HAM-A somatic and psychic factor scores by treatment group.

The change from baseline in HAM-A total score will be analyzed using the same MMRM as described in Section 5.3.1.2 for MADRS total score, with the continuous covariate “baseline MADRS total score” changed to “baseline HAM-A total score”.

As a sensitivity analysis, the change in HAM-A total score from baseline to each postbaseline time point will be analyzed using an ANCOVA model, using LOCF data. The derivation of the LOCF values is described in Section 5.3.1.2. The ANCOVA model will include factors for treatment, baseline insomnia status (present/absent), and baseline HAM-A total score as a continuous covariate. A 80% CI for the difference in LS Means will be calculated based on the contrast test statistic.

In addition, a frequency distribution over time of the HAM-A total score categories and HAM-A individual item scores at each time point will be provided by treatment group.

The shift in HAM-A total score categories (normal, mild, mild to moderate, moderate to severe, severe) from baseline to each time point will be presented by treatment group.

The correlations between HAM-A total score and MADRS total score will be evaluated using Pearson and Spearman correlation coefficients at each time point. These correlations will look at the correlations of the change from baseline. Scatter plots will also be presented.

5.3.5. Clinical Global Impression-Severity (CGI-S)

5.3.5.1. Definition

A secondary efficacy endpoint is the change from baseline to Weeks 12 and 24 in the CGI-S score. The CGI-S provides an overall clinician-determined summary measure of the severity of the subject's illness that takes into account all available information, including knowledge of the subject's history, psychosocial circumstances, symptoms, behavior, and the impact of the symptoms on the subject's ability to function. The CGI-S evaluates the severity of psychopathology on a scale of 1 to 7. Considering total clinical experience with the depression population, a subject is assessed on severity of illness at the time of rating according to: 1=normal (not at all ill); 2=borderline ill; 3=mildly ill; 4=moderately ill; 5=markedly ill; 6=severely ill; 7=among the most extremely ill patients. The CGI-S permits a global evaluation of the subject's condition at a given time.

The CGI-S change from baseline at Week 24 is calculated as (CGI-S score at Week 24 – Baseline CGI-S score). Change from baseline to other time points is calculated similarly. Negative changes in CGI-S score indicate improvement.

5.3.5.2. Analysis Methods

A frequency distribution over time of the CGI-S scores at Baseline, Week 2, Week 4, Week 6, Week 12, Week 18, Week 24, and at follow-up will be provided by treatment group. In addition, descriptive statistics of the actual values and the change from baseline will be presented by treatment group for observed case data.

The analysis of the change in CGI-S score from baseline to each postbaseline time point will be performed using an ANCOVA model on the ranks of the change in score with treatment and baseline insomnia status as factors, and unranked baseline CGI-S score as a covariate.

In addition, the correlation between CGI-S score and HAM-A total score and MADRS total score, separately, will be evaluated using Spearman correlation coefficients. These correlations will look at the correlations of the actual values at each time point, as well as the change from baseline. Scatter plots will also be presented.

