5.1. Analysis Specifications

5.1.1. Level of Significance

The primary efficacy endpoint will be evaluated at a two-sided significance level of 0.20. For all other efficacy endpoints, no multiplicity adjustment will be done and point estimates and confidence intervals will be presented.

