5.3.6. Patient Global Impression-Severity (PGI-S)

5.3.6.1. Definition

A secondary efficacy endpoint is the change from baseline to Weeks 12 and 24 in the PGI-S score. The PGI-S is a self-report scale to measure severity of illness (0=not depressed, 1=mildly depressed, 2=moderately depressed, 3=very depressed, 4=extremely depressed). Considering all aspects of depression, subjects will rate their severity on the PGI-S.

The PGI-S change from baseline at Week 24 is calculated as (PGI-S score at Week 24 – Baseline PGI-S score). Change from baseline to other time points is calculated similarly. Negative changes in PGI-S score indicate improvement.

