5.3.6.2. Analysis Methods

A frequency distribution over time of the PGI-S scores at Baseline, Week 2, Week 4, Week 6, Week 12, Week 18, Week 24, and at follow-up will be provided by treatment group. In addition, descriptive statistics of the actual values and the change from baseline will be presented by treatment group for observed case data.

The analysis of the change in PGI-S score from baseline to each postbaseline time point will be performed using an ANCOVA model on the ranks of the change in score with treatment and baseline insomnia status as factors, and unranked baseline PGI-S score as a covariate.

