5.4.1.2. Analysis Methods

Descriptive statistics of the actual values on Average predose, Week 6 (Average), Week 12 (Average), Week 18 (Average), and Week 24 (Average) and the change from Average predose to each postbaseline time point will be presented by treatment group for sSOL, sTST, sWASO, and s-nNAW.

The change from Average predose for sSOL, sTST, sWASO, s-nNAW, sFRESH and sQUAL will be analyzed using the same MMRM as described in Section 5.3.1.2 for MADRS total score, with the continuous covariate “baseline MADRS total score” changed to the corresponding baseline score for sSOL, sTST, sWASO, s-nNAW, sFRESH, and sQUAL respectively. For sFRESH and sQUAL, an additional analysis of the change from average predose to each postbaseline time point will be performed using an ANCOVA model on the ranks of the change in score with treatment and baseline insomnia status as factors, and unranked average predose score as a covariate.

In addition, for sFRESH and sQUAL, a frequency distribution of the average categorical response will be provided for Average predose, Week 6 (Average), Week 12 (Average), Week 18 (Average), and Week 24 (Average). In addition, the shift in average categorical response from Average predose to each of the postbaseline time points will be presented.

Descriptive statistics of the actual values on Average predose, Week 6 (Average), Week 12 (Average), Week 18 (Average), and Week 24 (Average) and the change from Average predose to each postbaseline time point will be presented by treatment group for average number of naps, the average total duration of naps (in minutes), the average number of drinks containing alcohol, and the average number of caffeinated drinks.

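### CGI-S and PGI-S are secondary endpoints whose only between-arm analysis is a per-visit rank ANCOVA, so the SAP specifies no treatment difference or confidence interval for them, although its Section 5.1.1 promises both

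*SAP*

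**What the plan says.** Both scales are declared secondary endpoints at two time points. SAP 5.3.5.1: "A secondary efficacy endpoint is the change from baseline to Weeks 12 and 24 in the CGI-S score". SAP 5.3.6.1: "A secondary efficacy endpoint is the change from baseline to Weeks 12 and 24 in the PGI-S score".

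The reporting rule in SAP 5.1.1 is general: "For all other efficacy endpoints, no multiplicity adjustment will be done and point estimates and confidence intervals will be presented". Protocol 11.3 is weaker and promises only nominal p-values for these endpoints.

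SAP 5.3.5.2 says the CGI-S analysis of change, made at each postbaseline time point in turn, "will be performed using an ANCOVA model on the ranks of the change in score with treatment and baseline insomnia status as factors", with the unranked baseline score as covariate. SAP 5.3.6.2 repeats this for PGI-S: "The analysis of the change in PGI-S score from baseline to each postbaseline time point will be performed using an ANCOVA model", again on ranks. The rest of these sections is frequency tables, arm-level descriptive statistics on observed cases and, for CGI-S, correlations with HAM-A and MADRS.

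For the exploratory diary items sQUAL and sFRESH, SAP 5.4.1.2 specifies the MMRM and then adds the rank method: "For sFRESH and sQUAL, an additional analysis of the change from average predose to each postbaseline time point will be performed".

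**The concern.** An ANCOVA on ranks tests for a difference and estimates a difference in mean rank. It does not estimate a difference in CGI-S or PGI-S points, and it gives no interval on that scale. As written, the two analysis sections cannot deliver what 5.1.1 promises.

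The second issue is missing data. Protocol 10.2 withdraws a subject from the study once study drug is stopped, so later scheduled ratings do not exist. The primary hypothesis is that the arms discontinue at different rates, and Protocol sections 6 and 10.2 name lack of efficacy as a reason for leaving. Dropout that is both unbalanced and related to severity is therefore foreseeable. The MMRM used for most other scales keeps incomplete subjects in the likelihood through their earlier visits. A separate ANCOVA at each visit, with no imputation rule, does not.

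At stake is whether the report can state how far the arms differ on clinician- and patient-rated global severity, and with what precision.

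**Working it through.** **1. Sections side by side**

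| Endpoint | SAP section | Between-arm analysis | Estimate and 80% CI |
|---|---|---|---|
| MADRS, HAM-A, QLDS, PROMIS-SD, PROMIS-SRI, SMDDS, SDMT, TMT-Part B, MADRS-6 | 5.3.1 to 5.3.12, 5.3.14 | MMRM of 5.3.1.2 | Yes |
| CGI-S, PGI-S | 5.3.5.2, 5.3.6.2 | Rank ANCOVA per time point | Not specified |
| sQUAL, sFRESH (exploratory) | 5.4.1.2 | MMRM plus rank ANCOVA | Yes, from the MMRM |

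HVLT-R (5.3.13.2) is a separate exception, with descriptive statistics only. LOCF is specified for MADRS, HAM-A and MADRS-6 change scores and BOCF for MADRS. Neither is specified for CGI-S or PGI-S.

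**2. The plan's own figure**

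Inputs (SAP 1.4): 50 per arm, hazard ratio 0.415, 50% discontinuation on quetiapine XR, one-sided 0.10, power about 92%.

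- JNJ-42847922 discontinuation: 1 − (1 − 0.50)^0.415 = 0.250.
- Expected events: 50 × 0.50 + 50 × 0.25 = 37.5.
- Schoenfeld power: Φ(√(37.5 × 0.25) × |ln 0.415| − 1.2816) = Φ(3.062 × 0.8795 − 1.2816) = Φ(1.411) = 0.921.

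The stated 92% reproduces, so the implied retention is the plan's own. The documents give no power or SD for CGI-S or PGI-S.

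**3. Who is left at the declared time points**

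- Week 24: 50 × 0.50 = 25 and 50 × 0.75 = 37.5, so 37.5 of 100 have left.
- Week 12, assuming a constant hazard: 50 × 0.50^0.5 = 35.4 and 50 × 0.75^0.5 = 43.3, so 21.3 of 100 have left.

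Half-width of an 80% CI for a mean difference, in SD units, is 1.2816 × √(1/n₁ + 1/n₂):

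- Week 24: 1.2816 × √(1/25 + 1/37.5) = 0.33.
- Week 12: 1.2816 × √(1/35.4 + 1/43.3) = 0.29.
- All 100 subjects: 1.2816 × √(2/50) = 0.26.

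**4. Possible bias at Week 24 (illustrative)**

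Assumptions not in the documents: no true treatment effect, SD 1.2, visit correlation 0.6, and a discontinuation log-hazard rising by 0.3 to 0.7 per SD of last observed severity. Total dropout is set to 25% and 50%.

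| Correlation | Baseline adjustment | Bias (points) |
|---|---|---|
| Exchangeable | none | about 0.08 to 0.17 |
| Exchangeable | yes | 0.03 to 0.07 |
| AR(1) | none | about 0.06 to 0.10 |
| AR(1) | yes | 0.05 to 0.09 |

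Repeat runs moved individual entries by 0.01 to 0.02. With zero slope the bias is zero. Here the bias favours quetiapine XR, because more severe subjects leave and more of them leave that arm. A repeated-measures estimate using earlier visits stayed within 0.01 of zero in the unadjusted settings, where dropout depends only on observed scores.

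A second simulation used a 1 to 7 integer score, 50 per arm and the planned rank ANCOVA with baseline. At two-sided 0.20 it rejected in 19% of trials when dropout was unrelated to score. With log-odds of 0.5 to 1 per SD of the previous score it rejected in 25% to 36%, with bias of 0.12 to 0.27 points. The sign reversed when the slope was reversed.

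**The case against.** A rank method is a defensible choice for a short ordinal scale, and its p-value would satisfy Protocol 11.3. That stands, which is why the rank test should be kept. It does not meet SAP 5.1.1.

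A reader might infer that the SAP excludes discontinuers outright. The documents do not support that. The observed-case wording is attached to the descriptive statistics. Use of observed data in the ANCOVA is inferred from the absence of any imputation rule. Discontinuers count until they leave, and a withdrawal assessment falling in the Week 12 or Week 24 window can count there. SAP Table 1 also lists an End point (DB) for both scales, defined in 2.8 as the last postbaseline double-blind result, which would keep them. Sections 5.3.5.2 and 5.3.6.2 do not say whether it is analysed, and it is not the declared endpoint.

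A reader might also infer that the plan yields no estimates at all, or is tilted towards quetiapine XR. Neither follows. Arm-level means and mean changes are planned. The direction of any bias depends on who leaves, and its size is modest: the 80% half-width at Week 24 is 0.33 × 1.2 = 0.40 points at the assumed SD, and baseline adjustment reduces the bias under exchangeable correlation.

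The diary comparison is not exact. sQUAL and sFRESH are averages over several mornings, so they are closer to continuous than a single integer rating. It still shows that the SAP accepts pairing an MMRM with a rank test. Finally, the PGI-S objective is worded as characterisation rather than comparison, and depressive severity has interval estimates from MADRS, MADRS-6 and SMDDS. That limits the consequence but does not supply the missing interval.

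**Conclusion.** The point holds in a limited form. For CGI-S and PGI-S the SAP specifies no between-arm estimate and no confidence interval, contrary to its own 5.1.1. This rests on the text alone.

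The missing-data part is conditional. Without an imputation rule or repeated-measures model, subjects who have left do not contribute at Weeks 12 and 24 unless End point (DB) is analysed. On the planning assumptions about 25 versus 37.5 of 50 remain at Week 24. Any bias needs dropout to depend on severity. Its size, roughly 0.03 to 0.17 points in the SD 1.2 simulations, and its direction rest on assumptions outside the documents.

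This is a desirable improvement to two secondary analyses in an exploratory trial.

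**What to change.** In SAP 5.3.5.2 and 5.3.6.2, add the MMRM of 5.3.1.2 with the scale's own baseline as covariate. Report the LS mean difference and 80% CI at Weeks 12 and 24. Keep the rank ANCOVA as the robustness check, the same pairing that 5.4.1.2 uses for sQUAL and sFRESH. State whether the rank ANCOVA is also run on End point (DB).

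Before any PGI-S mean difference is reported, reconcile its coding: Protocol 9.2.3 and SAP Table 3 give four levels scored 1 to 4, while SAP 5.3.6.1 gives five levels scored 0 to 4.

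The cost is two further runs of a model already programmed, plus a short text correction. The downside is that the added model treats a short ordinal scale as numeric; the retained rank test covers that. The MMRM also relies on dropout being explained by observed scores, as it does for the other scales.

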5.3.6. Patient Global Impression-Severity (PGI-S)

5.3.6.1. Definition

A secondary efficacy endpoint is the change from baseline to Weeks 12 and 24 in the PGI-S score. The PGI-S is a self-report scale to measure severity of illness (0=not depressed, 1=mildly depressed, 2=moderately depressed, 3=very depressed, 4=extremely depressed). Considering all aspects of depression, subjects will rate their severity on the PGI-S.

The PGI-S change from baseline at Week 24 is calculated as (PGI-S score at Week 24 – Baseline PGI-S score). Change from baseline to other time points is calculated similarly. Negative changes in PGI-S score indicate improvement.

5.3.6.2. Analysis Methods

A frequency distribution over time of the PGI-S scores at Baseline, Week 2, Week 4, Week 6, Week 12, Week 18, Week 24, and at follow-up will be provided by treatment group. In addition, descriptive statistics of the actual values and the change from baseline will be presented by treatment group for observed case data.

The analysis of the change in PGI-S score from baseline to each postbaseline time point will be performed using an ANCOVA model on the ranks of the change in score with treatment and baseline insomnia status as factors, and unranked baseline PGI-S score as a covariate.

5.3.7. Quality of Life in Depression Scale (QLDS)

5.3.7.1. Definition

A secondary efficacy endpoint is the change from baseline to Weeks 12 and 24 in the QLDS score. The QLDS is a disease specific patient-reported outcome (PRO) designed to assess health related quality of life in patients with MDD. The instrument has a recall period of "at the present time", contains 34-items with "true"/"not true" response options, and takes approximately 5 to 10 minutes to complete.

Each statement on the QLDS is given a score of "1" or "0". A score of "1" is indicative of adverse quality of life. All item scores are summed to give a total score that ranges from 0 (good quality of life) to 34 (very poor quality of life).

As the measure contains positive as well as negative items, item scores are not always in the same order - that is, not all 'true' responses are allocated a score of "1". The scores for each item can be found in Attachment 1.

Imputation of the total score will be performed only when between 1 to 6 items are missing responses. If 7 or more items are missing, the total score will be left missing. The total score will be imputed as follows:

$$T = \frac{x}{34 - m} \times 34$$

where T is the final total score, x is the item summation score, and m is the number of missing items.

5.3.7.2. Analysis Methods

Descriptive statistics of the actual values on Baseline, Week 2, Week 4, Week 6, Week 12, Week 18, and Week 24 and the change from baseline to each postbaseline time point will be presented for QLDS total score by treatment group.

The change from baseline in QLDS total score will be analyzed using the same MMRM as described in Section 5.3.1.2 for MADRS total score, with the continuous covariate "baseline MADRS total score" changed to "baseline QLDS total score".

Frequency distributions of the QLDS individual items will be provided at each assessment time point by treatment group.

